	
 
• Change in percent of glucose values of CGM measurements (in a subset of patients) within targeted range of 71 and 180 mg/dl (4.0 and 10.0 mmol/l) from a one or two week period of week -2 to week 0 (baseline) to a one or two week period of week 22 to week 24;
 
• Change in 3-day average 7-point SMBG from baseline to week 24;
 
• Change in 3-day coefficient of variation (CV) of 7-point SMBG from baseline to week 24;
 

Tertiary Endpoints	
 
• Change in A1C from baseline to week 12;
 
• Change in average glucose values of CGM measurements (in a subset of patients) from a one or two week period of week -2 to week 0 (baseline) to a one or two week period of week 22 to week 24.
 
• Change in percent of glucose values of CGM measurements (in a subset of patients) <math>\leq</math> 70 mg/dl (<math>\leq</math> 3.9 mmol/l) and percent of values <math>></math> 180 mg/dl (<math>></math> 10.0 mmol/l) from a one or two week period of week -2 to week 0 (baseline) to a one or two week period of week 22 to week 24;
 
• Change in FPG from baseline to week 24;
 
• Change in 3-day insulin doses (total daily dose, basal dose, bolus dose) from baseline to week 24.
 

Patient Reported Outcomes	
 
• Change in treatment satisfaction for insulin delivery from baseline to week 24;
 
• Change in patient quality of life from baseline to week 24;
 
• Patient experience survey at week 24;
 
• Patient insulin usage survey at week 12 and 24.
 

Healthcare Provider Reported Outcomes	
 
• HCP experience survey at week 24.
 

Endpoint Evaluation at Week 44	
Secondary Endpoints	
 
• Change in A1C from baseline to week 44;
 
• Proportion of patients with A1C <math>\leq</math> 7.0% at week 44;
 
• Change in 3-day average 7-point SMBG from baseline to week 44;
 
• Change in A1C from week 24 to week 44.
 

Tertiary Endpoints	
 
• Change in A1C from baseline to week 36;
 
• Change in 3-day CV of 7-point SMBG from baseline to week 44.
 
• Change in FPG from baseline to week 44;
 

	
 
Change in 3-day insulin doses (total daily dose, basal dose, bolus dose) from baseline to week 44.
 

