#### Efficacy Analysis Plan

Differences between arms (Finesse arm versus pen arm) at week 24 will be analyzed using analysis of covariance (ANCOVA) model with the baseline A1C value as the covariate; the 2-sided 95% confidence interval of the difference will be computed using the model. The non-inferiority of Finesse to pen will be concluded if the upper bound of the 95% 2-sided confidence interval for change in A1C is less than the inferiority margin of 0.4%. This test is the same as a 1-sided test with an alpha of 0.025. Superiority of Finesse will be tested if non-inferiority is shown.

Each of the secondary and tertiary endpoints at week 24 and week 44 will be tested for superiority of the Finesse arm to the pen arm, but the tests will be interpreted inferentially only if non-inferiority is demonstrated with respect to the primary endpoint. Otherwise, the p-values and 95% confidence intervals for the secondary and tertiary endpoints will be considered to be nominal. The continuous endpoints will be analyzed using the same ANCOVA model described for the primary endpoint. The categorical endpoints will be analyzed using a Cochran-Mantel-Haenszel test. The Type 1 error rate will be at 0.05.

To evaluate durability of effect of using Finesse versus pen, change in A1C from 24 week to 44 week will be analyzed by treatment groups using t-test for each treatment arm.

Other general considerations for the statistical analysis will include descriptive statistics (sample size, mean, SD, median, minimum, and maximum) for continuous variables and 95% CI of the mean, and, where appropriate, the percentage values for categorical variables, and tests of significance between treatment arms including p-value and 95% CI.

Additional Analyses

Analyses will also be performed to examine the relationships between variables known to be associated. In particular, the relationship between A1C and severe hypoglycemiaiii, the relationship between A1C and weight change, and the relationship between A1C and adherence measures will be described in each group. These analyses will be descriptive, primarily using categorical cross-classifications to examine whether any shifts in hypoglycemia, weight change, or adherence measures are consistent with expected changes due to improved glycemic control.

---

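### Once A1C non-inferiority is shown, A1C superiority and every secondary and tertiary test become inferential at full alpha, so error across these superiority claims is not controlled

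*Combined protocol and SAP*

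**What the plan says.** The Efficacy Analysis Plan contains one multiplicity rule. For the secondary and tertiary endpoints, "the tests will be interpreted inferentially only if non-inferiority is demonstrated with respect to the primary endpoint". If that gate fails, "the p-values and 95% confidence intervals for the secondary and tertiary endpoints will be considered to be nominal". If it opens, "Each of the secondary and tertiary endpoints at week 24 and week 44 will be tested for superiority of the Finesse arm" over the pen arm. For the primary endpoint, "Superiority of Finesse will be tested if non-inferiority is shown". The only statement about error is "The Type 1 error rate will be at 0.05", with no indication of sidedness or of whether it applies per test or across tests.

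The endpoint lists give eight secondary bullets (four at week 24, four at week 44) and nine tertiary bullets (five and four). One secondary, "Change in A1C from week 24 to week 44", also has its own analysis: "change in A1C from 24 week to 44 week will be analyzed by treatment groups using t-test for each treatment arm".

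The Study Objectives also set out to demonstrate better patient-reported outcomes and provider and patient preference for Finesse. The multiplicity rule gives those results no status.

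**The concern.** The plan distinguishes inferential from nominal results, so it evidently intends some secondary findings to count as demonstrated. The gate alone cannot support that. It limits false claims when Finesse is worse than the pen by 0.4% or more. It does little when the devices are equal, because equal devices usually pass and every superiority null hypothesis is then true while each is tested at full alpha.

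The step from non-inferiority to superiority on A1C inflates nothing by itself. The inflation comes from opening all the other endpoints on non-inferiority alone, alongside A1C superiority. At stake is which superiority results the report may call demonstrated.

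**Working it through.** **Inputs.** Sample Size Determination: margin 0.4%, SD 1.2%, assumed difference -0.1%, 125 completers per arm, 312 enrolled (156 per arm). Study Design: 50 CGM patients per arm. Efficacy Analysis Plan: one-sided 0.025 for non-inferiority. Assumed, because the documents are silent: one-sided 0.025 for each superiority test, and patient-level correlation r between endpoints of 0, 0.5, 0.7 or 0.9.

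**The plan's own figure.** n per arm = 2 × (1.960 + 1.282)² × 1.2² / 0.5² ≈ 121.0, rounded up to 122, or 244 in total against 250 stated. At 125 per arm, SE = 1.2 × √(2/125) = 0.1518 and power = Φ(0.5/0.1518 − 1.960) = 90.9%. Then 250/0.80 = 312.5 against 312. The sample size reproduces.

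**Gate when the devices are equal.** At 125 per arm: Φ(0.4/0.1518 − 1.960) = Φ(0.675) = 75.0%. The primary analysis uses the mITT set, which could approach 156 per arm. There SE = 1.2 × √(2/156) = 0.1359 and the gate passes Φ(0.984) = 83.7% of the time.

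**Family.** A1C superiority plus seven between-arm secondaries:
- Week 24: A1C responders, CGM time in range, mean SMBG, SMBG CV.
- Week 44: A1C change, A1C responders, mean SMBG.

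The week 24-to-44 change is left out as within-arm.

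**Exact result at r = 0.** P(gate passed and at least one false Finesse claim) = 0.025 + (P(gate) − 0.025) × (1 − 0.975⁷), with 1 − 0.975⁷ = 0.1624.
- 125 per arm: 0.025 + 0.7252 × 0.1624 = 14.3%.
- 156 per arm: 0.025 + 0.8124 × 0.1624 = 15.7%.

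**Correlated case.** This used simulated normal test statistics (1,000,000 runs per setting) with the gate applied to the A1C statistic. The CGM statistic comes from 100 patients, so its correlation with a full-sample test is r × √(100/250) = 0.63r at 125 per arm, or r × √(100/312) = 0.57r at 156.

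| Patient-level r | 0 | 0.5 | 0.7 | 0.9 |
|---|---|---|---|---|
| 125 per arm | 14.3% | 12.7% | 10.3% | 7.1% |
| 156 per arm | 15.7% | 12.9% | 10.6% | 7.4% |

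The reference is 2.5%. Independence (r = 0) is an upper illustration, since several endpoints are closely related.

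**Adding tertiary endpoints.** With all 17 bullets plus A1C superiority (18 tests, 125 per arm), the r = 0 figure is 0.025 + 0.7252 × (1 − 0.975¹⁷) = 27.9%. At a common correlation of 0.7 it is about 14%.

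**With Holm over the eight tests** at two-sided 0.05, gate included, the chance of a false claim for Finesse is about 2.0% or less at 125 per arm across these correlations, and at most about 2.1% at 156.

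**The case against.** The strongest reply is that the consequences are limited. The device is already cleared, no regulatory claim is tied to a secondary result, and the 0.05 sentence can be read as a per-test level, since it never says familywise. All of that stands, and it limits the severity. It does not remove the problem: under a per-test reading, passing non-inferiority still makes even tertiary results inferential with nothing controlling error across them.

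A second reply is that the endpoints are correlated. They are, and this lowers the figure, but at r = 0.9 it is still more than twice 2.5%.

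A third concerns the count. Because the superiority sentence says each endpoint, a reader might infer that the week 24-to-44 A1C change is a ninth between-arm test. The documents point the other way: the durability objective concerns maintenance with both devices, and the analysis named for it is a t-test in each arm. Two other drafting questions, whether "Change in A1C from baseline to week 12" and its week 36 counterpart fall within the weeks 24 and 44 rule and which direction favours Finesse for insulin dose, affect only the tertiary count.

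Finally, putting A1C superiority into a shared family costs it power that a simple step from non-inferiority would not. That is fair, and the fix offers an alternative.

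**Conclusion.** The concern holds. The plan does not control error across the superiority claims that open after non-inferiority. With equal devices, the chance of at least one false Finesse claim among A1C superiority and seven secondaries is about 7% to 14% at 125 per arm and 7% to 16% at 156, against 2.5%. The structural point follows from the text. The size depends on the assumed sidedness, correlations and SD.

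Two stronger readings are not supported. A reader might compute a 60% error rate from 18 independent two-sided tests at 0.05 (1 − 0.95¹⁸ = 60.3%). That takes the gate as already passed, counts results against Finesse and treats related endpoints as independent. A reader might also infer that the primary result is compromised. It is not: the non-inferiority test, its one-sided 0.025 level and the 250/312 sample size are unaffected. If Finesse is truly worse by the margin or more, any inferential claim must first pass a gate that opens at most 2.5% of the time.

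This should be fixed, as a matter of what the report may claim.

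**What to change.** Keep the non-inferiority gate and the sample size. Before comparative data are seen, amend the Efficacy Analysis Plan as follows:

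- State that the week 24-to-44 A1C change is a within-arm, descriptive analysis.
- After the gate, apply one prespecified familywise procedure to A1C superiority and the seven between-arm secondaries, for example Holm at two-sided 0.05 (first threshold 0.05/8 = 0.00625). Claim superiority only in the direction favouring Finesse.
- Report all tertiary, patient-reported and provider-reported tests as nominal with 95% confidence intervals. The plan already defines that status.
- Replace the Type 1 error sentence with a statement that familywise error is controlled at two-sided 0.05 over A1C superiority and the between-arm secondary endpoints.

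**Cost.** Tertiary endpoints lose inferential status. At the first Holm step (critical value 2.734), a secondary with 80% power at two-sided 0.05 falls to Φ(2.802 − 2.734) = 53%. The 80% is an illustration, since the documents give no power for secondaries. A1C superiority at the assumed -0.1% (0.1/0.1518 = 0.659) falls from Φ(0.659 − 1.960) = 10% to Φ(0.659 − 2.734) = 2%.

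Holm is one valid choice among several. To keep A1C superiority at full alpha, the sponsor could test it directly after non-inferiority and report all secondaries as nominal, which also controls error. Placing the secondaries behind A1C superiority in a fixed sequence is less attractive, because at -0.1% they would be reached only about 10% of the time.

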Dosage and Administration	
At randomization, total daily dose (TDD) of insulin will be divided as 50:50, basal: bolus (Note: For those subjects with a screening A1C of <math><9\%</math>, the TDD is to be reduced by 10% prior to splitting the dose 50:50, basal: bolus, in order to avoid potential for hypoglycemia at institution of new regimen). Basal insulin therapy for each group will be titrated using a simple algorithm by chart to adjust by 2U increments to achieve pre-morning meal fasting plasma glucose (FPG) target of 71-130 mg/dl (4.0-7.2 mmol/l). Bolus insulin dosing will start with fixed pre-meal doses (divided equally between morning meal, midday meal, and evening meal). Prandial insulin therapy for each group will be titrated using a simple algorithm by chart to adjust by 2U increments based on pre-midday meal and pre-evening meal self-monitoring blood glucose (SMBG) target of 71-130 mg/dl (4.0-7.2 mmol/l) and bedtime SMBG target of 71-130 mg/dl (4.0-7.2 mmol/l): pre-morning meal dose will be titrated based on pre-midday meal SMBG; pre-midday meal dose will be titrated based on pre-evening meal SMBG; pre-evening meal dose will be titrated based on bedtime SMBG. For basal insulin, all patients will use Lantus® (Glargine) by a pen (SoloStar®) before evening meal or at bedtime. For bolus insulin, patients will use Finesse containing rapid-acting NovoLog®/NovoRapid® (Aspart) or the FlexPen®. Patients will discontinue the following AHA: Sulfonylureas, Meglitinides, GLP-1 agonists, bromocriptine, and DPP-4 inhibitors that have not been studied in combination with insulin, namely, saxagliptin and linagliptin. Patients on the following AHAs will continue them in their current doses: Biguanides, Alpha-glucosidase inhibitors, SGLT2 inhibitors, Thiazolidinediones, and DPP-4 inhibitors that have been studied and approved for use in combination with insulin, namely, sitagliptin, alogliptin, and vildagliptin.

Endpoint Evaluation at Week 24	
Primary Endpoint	Change in A1C from baseline to week 24, comparing Finesse versus Pen.
Secondary Endpoints	
 
• Proportion of patients with A1C <math>\leq 7.0\%</math> at week 24;
 

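### Insulin-dose endpoints fall under the superiority rule with no favourable direction defined, and the planned ANCOVA does not adjust for prior dose

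*Combined protocol and SAP*

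**What the plan says.** All references are to the combined protocol and SAP.

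- **Testing rule** (Efficacy Analysis Plan): "Each of the secondary and tertiary endpoints at week 24 and week 44 will be tested for superiority of the Finesse arm to the pen". The one condition is that "the tests will be interpreted inferentially only if non-inferiority is demonstrated with respect to the primary endpoint"; otherwise the results are nominal. The Type 1 error rate is 0.05, with no statement of one or two sides for these tests.
- **Endpoints** (Tertiary Endpoints, weeks 24 and 44): "Change in 3-day insulin doses (total daily dose, basal dose, bolus dose) from baseline to week 24", and "Change in 3-day insulin doses (total daily dose, basal dose, bolus dose) from baseline to week 44". No favourable direction is given for any of the three doses.
- **Model** (Efficacy Analysis Plan): continuous secondary and tertiary endpoints use the ANCOVA of the primary endpoint, which has baseline A1C as its covariate.
- **Starting doses** (Dosage and Administration): "At randomization, total daily dose (TDD) of insulin will be divided as 50:50, basal: bolus". If screening A1C is below 9%, "the TDD is to be reduced by 10% prior to splitting the dose 50:50, basal: bolus". No difference by arm is given.
- **Titration** (same section): "Basal insulin therapy for each group will be titrated using a simple algorithm by chart to adjust by 2U increments", and "Prandial insulin therapy for each group will be titrated using a simple algorithm by chart to adjust by 2U increments". Both are steered to glucose targets.

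**The concern.** A superiority test needs a direction that counts as better. A1C, fasting glucose, time in range and SMBG variability have an evident one; insulin dose does not. A higher bolus dose on Finesse could reflect fewer omitted meal doses, or more insulin needed for the same effect. A lower dose could reflect efficiency or under-treatment. If the direction is left open until the data are seen, either sign can be presented as an advantage of Finesse.

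Dose also helps in reading the primary result. Both arms are titrated to the same glucose targets, so similar A1C can be reached at different doses. The Additional Analyses relate A1C to severe hypoglycemia, weight change and adherence, but not to insulin dose.

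The second part is the model. Starting basal and bolus doses are computed from the prior total daily dose, yet that dose is not a covariate if the plan is read literally.

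**Working it through.** **1. The plan's own figure.** The documents give no figure for the dose endpoints. The one to reproduce is the primary sample size (margin 0.4, assumed difference -0.1, SD 1.2, one-sided 0.025, power 90%):

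n per arm = 2 × 1.2² × (1.960 + 1.282)² / (0.4 + 0.1)² = about 121.1, rounded up to 122, against the stated 125. Power at 125 per arm is 90.9%, against 90%. 250/0.80 = 312.5, against 312. The figures reproduce, and nothing below alters them.

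**2. Tests affected.** 3 doses × 2 time points = 6.

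**3. Effect of an open direction.** Assume a two-sided 0.05 test and no true difference. With one direction fixed, the chance of a false superiority label is 0.025 per endpoint. If either sign qualifies, it is 0.025 + 0.025 = 0.05. Across six independent tests the chance of at least one is 1 - 0.95⁶ = 26.5%. The dose endpoints are correlated, so that last figure is only illustrative.

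**4. Conversion at randomization, per 100 U of prior dose.** Patients enter on basal insulin and start bolus in the trial, so baseline bolus is taken as zero and prior basal dose equals prior total dose.

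| Screening A1C | Starting basal | Starting bolus | Change in basal | Change in bolus | Change in total |
|---|---|---|---|---|---|
| 9% or above | 50 | 50 | -50 | +50 | 0 |
| Below 9% | 45 | 45 | -55 | +45 | -10 |

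Each starting dose is therefore 45% to 50% of prior dose.

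**5. Does the conversion create a between-arm difference?** Two arms of 125 were simulated under one shared rule and compared by t-test. Assumed: prior dose mean 50 U, SD 15; 55% of patients below 9%; titration of +10 U basal (SD 15) and +15 U bolus (SD 20).

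- Equal titration: within-arm changes were basal -16.6 U, bolus +38.8 U, total +22.2 U. The between-arm difference was about 0, with rejection in 5.0% to 5.6% of runs.
- 10 U more bolus in one arm: a difference of about 10 U, detected in 97% (bolus) and 89% (total) of runs.

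The shared conversion cancels, and a real difference remains visible.

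**6. What omitting prior dose costs.** Chance imbalance in mean prior dose has SE = SD × √(2/125). The documents give no SD, so a range is assumed. About half of the imbalance carries into the starting basal or bolus change.

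| Assumed SD of prior dose | SE of imbalance | 95% range (1.96 × SE) | Half carried over |
|---|---|---|---|
| 10 U | 1.3 U | ±2.5 U | ±1.2 U |
| 15 U | 1.9 U | ±3.7 U | ±1.9 U |
| 20 U | 2.5 U | ±5.0 U | ±2.5 U |

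The share of outcome variance due to prior dose, with titration independent of it and SD 15 U for prior dose, is:

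- bolus: 7.5² / (7.5² + 20²) = 56.25/456.25 = 12%;
- basal: 7.5² / (7.5² + 15²) = 56.25/281.25 = 20%;
- total: at most 1.5² / (1.5² + 15² + 20²) = 2.25/627.25 = 0.4%.

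The gain is modest for basal and bolus and negligible for change in total dose. The imbalance is ordinary sampling error that the unadjusted interval already covers, so this is lost precision, not bias.

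**The case against.** The strongest reply is that little is at stake. The endpoints are tertiary and are read inferentially only after primary non-inferiority. The ANCOVA yields a two-sided 95% CI, and the plan also calls for descriptive statistics and between-arm p-values, so the sign and size of any dose difference will be reported. Total dose and A1C are both endpoints at weeks 24 and 44, so a finding of equal A1C at higher dose would not be concealed. The insulin usage surveys and adherence analyses help to explain a difference. All of this stands, and it keeps the point minor. It does not supply a direction, and it does not remove the inferential superiority label.

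On the covariate, one could read the same ANCOVA model as adjusting each endpoint for its own baseline value. For total and basal dose that would amount to the adjustment proposed here. For bolus it would not, because baseline bolus is about zero for everyone and cannot act as a covariate.

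Two stronger readings are tempting and should not be drawn:

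- A reader might infer that the conversion rule drives the between-arm result. The rule is the same in both arms and cancels under 1:1 randomization. It shapes the within-arm change on day 1, but the endpoints come after 24 and 44 weeks that include titration. The documents do not show how much of the final change it explains, and it moves total dose by only 0 to -10%.
- A reader might infer that a dose difference has no clinical meaning. It does have meaning: it describes insulin use by device and helps to interpret A1C. What it cannot carry, without a stated direction, is the word superiority.

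**Conclusion.** The point holds as a minor one. The text makes six dose comparisons into superiority tests without saying what superior means, and read literally it adjusts them for baseline A1C only. The first part rests on the wording alone. The second rests on baseline bolus being about zero, which is inferred from the population and design, and its size rests on assumed SDs: roughly 12% of variance for bolus and 20% for basal at a prior-dose SD of 15 U, and almost nothing for change in total dose. The primary test, its alpha and the sample size are unaffected.

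**What to change.** In the Efficacy Analysis Plan:

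1. Exempt change in total, basal and bolus dose at weeks 24 and 44 from the superiority rule.
2. Report each as a two-sided between-arm difference with 95% CI, from an ANCOVA that includes pre-randomization total daily dose, and make no superiority claim. With that covariate in the model and baseline bolus at zero, analysing the change or the attained dose gives the same treatment difference.
3. Show these differences beside the A1C result at the same time point, so that equal A1C at unequal dose is plain.

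The cost is SAP wording, settled before any comparison by arm is seen. No new data are needed: the prior dose is required for the split at randomization and for the change score. The sponsor gives up only the option of a superiority statement on dose.

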Study Design	
A randomized, open-label, 2-arm parallel study comparing glycemic control, patient satisfaction, and quality of life (QOL) of using Finesse versus pen to initiate and manage bolus insulin dosing in 312 patients, male and female, ages 22 to 75 years of age with T2DM not achieving glycemic targets on basal insulin with/without AHA. After a 4-week screening/baseline period, patients will be randomized 1:1 (balanced by study center) to either the Finesse arm or the pen arm to initiate bolus insulin using a simple bolus dosing algorithm and followed for a 44-week intervention period. After the final endpoint evaluation at week 44, patients will crossover to the alternate bolus insulin delivery device for 4 weeks and complete a patient preference survey at week 48.
 
The study will be conducted in the following periods: Screening Visit 1 (Week -4 to -3); Baseline Visit 2A (Week -2); Randomization Visit 3 (Week 0) to include insulin dosage optimization;i,1 Phone Calls Insulin Titration (Weeks 1, 2, 3, 6, 8); Follow-up Visits 4 (Week 4), 5 (Week 12), 6C (Week 24), 7 (Week 36), 8 (Week 44), and 9 (Week 48). Visits 2B (Week -1), 6A (Week 22), and 6B (Week 23): Only the subset of patients performing continuous glucose monitoring (CGM) (50 patients per arm) will have additional visits for performing blinded CGM assessments.

Study Sites	A multicenter study (approximately 50 sites). Sites and patients will be approximately divided between the US and EU.
Patient Population	A total of approximately 312 enrolled adults, male and female, aged 22-75 years, body mass index of $\leq 40 \text{ kg/m}^2$ , with T2DM not achieving glycemic targets (A1C 7.5-11.0%)

i Educational materials specifically designed for this study based on the International Diabetes Center simple algorithm for adjustment of insulin in Type 2 diabetes. Patients will record SMBG before meals and bedtime, and insulin doses.

	using basal insulin ( $\geq 0.3$ U/kg/day) with/without AHA based on the participant's medical needs.
Duration of Patient Participation	Total duration of participation by each patient is expected to be approximately 52 weeks.

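### As written, the non-A1C continuous endpoints are adjusted for baseline A1C and not for their own baseline, which costs precision but not validity

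*Combined protocol and SAP*

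**What the plan says.** The Efficacy Analysis Plan specifies the primary comparison as an "analysis of covariance (ANCOVA) model with the baseline A1C value as the covariate". For the secondary and tertiary endpoints at weeks 24 and 44 it adds: "The continuous endpoints will be analyzed using the same ANCOVA model described for the primary endpoint". No other covariate is named anywhere in the document.

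The same section tests each of these endpoints for superiority of Finesse and treats the tests as inferential once non-inferiority holds on the primary endpoint.

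The endpoint lists for weeks 24 and 44 include several continuous changes that are not A1C:

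- the mean of the SMBG profiles
- their variability: "Change in 3-day coefficient of variation (CV) of 7-point SMBG from baseline to week 24"
- fasting glucose: "Change in FPG from baseline to week 24"
- changes in insulin dose
- three CGM percentages and the CGM average, each measured from "week -2 to week 0 (baseline) to a one or two week period of week 22 to week 24"

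SMBG mean, SMBG CV, FPG and dose are evaluated again at week 44. Under Study Design, CGM is limited to a subset of 50 patients per arm.

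**The concern.** For an A1C change from baseline, baseline A1C is the endpoint's own baseline and the model is the usual one. For time in range, SMBG variability, FPG or insulin dose it is a different variable, perhaps only loosely related to the outcome. A change score analysed without its own baseline as covariate carries baseline noise that ANCOVA would remove.

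The endpoint definitions already require those baselines, so the information is collected but not used. What is at stake is power and interval width for endpoints the plan intends to test, chiefly the CGM endpoints with their small subset.

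The sentence can also be read as the same form of model with the matching baseline. Two readings give two p-values per endpoint, and in an open-label trial that choice should be fixed beforehand.

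Not affected are the A1C changes from baseline (weeks 12, 24, 36 and 44), the proportions with A1C at or below 7.0%, and the within-arm t-tests of A1C change from week 24 to week 44. Change in bolus dose is also unaffected if its baseline is the pre-bolus period, when every patient's value is zero.

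**Working it through.** **The plan's own figure.** The only sample size calculation is for the primary endpoint. With margin 0.4, true difference -0.1, SD 1.2, one-sided alpha 0.025 and 90% power, n per arm = 2 × 1.2² × (1.960 + 1.282)² / 0.5² ≈ 121.1, so 122, against 125 stated. Power at 125 per arm is 0.909. 250/0.8 = 312.5, against 312 stated. These figures reproduce and do not depend on this point. The plan states no power for the affected endpoints.

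**Inputs.** From the document: 1:1 randomization, baseline A1C as the only covariate, 50 per arm in the CGM subset. Assumed, because the document gives no correlations:

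- equal SDs at baseline and follow-up, scaled to 1
- rho = correlation of the endpoint's baseline with its follow-up value
- r and s = correlation of baseline A1C with the endpoint's baseline and follow-up, taken as (0.5, 0.3) or (0.3, 0.15)

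**Formulas** (error variance for the treatment comparison):

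- Plan as written, change adjusted for A1C only: Vw = 2(1 - rho) - (s - r)²
- Own baseline only: Vo = 1 - rho²
- Both covariates: Vb = 1 - (rho² + s² - 2·rho·r·s)/(1 - r²)

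Example at rho = 0.4, r = 0.5, s = 0.3: Vw = 1.20 - 0.04 = 1.16; Vo = 1 - 0.16 = 0.84; Vb = 1 - (0.16 + 0.09 - 0.12)/0.75 = 0.827. So Vw/Vo = 1.381 and Vw/Vb = 1.403.

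Power when own-baseline ANCOVA has 80%: Φ(2.80/√(Vw/Vo) - 1.96). Equivalent CGM sample size per arm: 50/(Vw/Vo).

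| rho | Vw/Vo, (0.5, 0.3) | Vw/Vo, (0.3, 0.15) | Power instead of 80% | Equivalent n of 50 |
|---|---|---|---|---|
| 0.2 | 1.625 | 1.643 | 59% | 30-31 |
| 0.4 | 1.381 | 1.402 | 66% | 36 |
| 0.6 | 1.188 | 1.215 | 72-73% | 41-42 |
| 0.7 | 1.098 | 1.132 | 75-76% | 44.2-45.5 |
| 0.9 | 0.842 | 0.934 | above 80% | above 50 |

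If r = s, the ratio is 2/(1 + rho): 1.18 at rho 0.7 and 1.05 at 0.9.

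**Why keep both covariates.** In the last row own baseline alone is less precise than A1C alone. Apart from the degree of freedom, the model with both cannot be less precise than either. Vw/Vb is 1.40 at rho 0.4, 1.10 to 1.14 at 0.7 and 1.00 to 1.02 at 0.9.

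**CGM subset.** The difference detectable with 80% power is 2.80 × √(2V/50). At rho 0.4 it is 0.51 SD with own baseline and 0.60 to 0.61 SD as written.

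**Second derivation.** Assume instead that A1C relates to follow-up only through the endpoint's baseline (s = r·rho). Then Vw/Vo = [2(1 - rho) - r²(1 - rho)²]/(1 - rho²). Over rho 0.3 to 0.7 and r 0 to 0.7 the written model has 9% to 54% more error variance, and power of 62% to 77% instead of 80%. At rho = r = 0.5 the excess is 25% and power is 71%.

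**Validity.** In 20,000 simulated null trials with 50 per arm and (r, s) = (0.5, 0.3), type I error at rho 0.4 was 0.051 as written and 0.050 with own baseline, with mean difference 0.000 in both; at rho 0.7 it was 0.049 in both. Simulated variance ratios were 1.40 and 1.10, matching the formulas. Under the second set of assumptions (10,000 trials per scenario, 250 or 100 patients), type I error as written was 0.0486 to 0.0495, and a true effect of 0.35 was estimated at 0.348 to 0.352.

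**The case against.** The strongest reply is that, for the primary endpoint, baseline A1C *is* the endpoint's own baseline, so the same model may simply mean treatment plus the matching baseline. That reading is reasonable. The text does not say it, and the same added sentence settles it, so the need to edit remains.

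Second, the trial is powered only for the primary endpoint and most affected items are tertiary, so the fall from 80% is measured against a benchmark the plan never claims. That is correct and limits the severity. Even so, CGM time in range, SMBG mean and SMBG CV are secondary endpoints to be tested for superiority.

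Third, the size rests on assumed correlations and equal SDs. This also stands. With r = 0.7 and s = 0.3, Vw/Vo is 1.24 at rho 0.4, 1.00 at 0.6 and 0.86 at 0.7; against both covariates it is 1.24, 1.05 and 1.00. At rho 0.4 with the (r, s) pairs in the table, the ratio is about 1.1 if the follow-up SD is 1.4 times the baseline SD, and about 2.1 if it is 0.7 times. The ratios show a range and are not forecasts.

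Fourth, the CGM figures assume 50 analysed per arm. If 50 is the number starting and the plan's 20% discontinuation applies, 50 × 0.8 = 40 remain, and at rho 0.4 the detectable difference is 0.57 against 0.68 SD. The ratio does not change.

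Finally, the plan does not define baseline for the dose endpoints, so bolus dose at week 0 could vary between patients. Nor does it say whether the sentence covers the changes in treatment satisfaction and quality of life; if it does, the same point applies to them.

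**Conclusion.** The point holds. As written, the plan adjusts the non-A1C continuous change endpoints for a covariate that will usually be weaker than one the trial already collects, and nothing else in the document corrects this. The comparisons remain unbiased over randomization with correct type I error; a chance imbalance in an endpoint's own baseline would go uncorrected.

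Against the model with both covariates, the loss under the tabulated (r, s) pairs is about 40% in error variance at rho 0.4, 10% to 14% at 0.7 and 0% to 2% at 0.9. Confidence in the size is moderate, because every correlation is assumed. The primary analysis and sample size are untouched. This should be changed before analysis, but it does not threaten the trial's main conclusion.

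**What to change.** Replace the sentence on continuous endpoints with wording such as: *Each continuous change-from-baseline endpoint will be analysed by ANCOVA with treatment, the pre-randomization value of that endpoint, and baseline A1C as terms. Change in bolus dose will be adjusted for baseline total daily insulin dose.* For A1C change endpoints the two covariates coincide and the model stays as it is.

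For any between-arm comparison of A1C change from week 24 to week 44, state that the covariate is the pre-randomization A1C and not the week 24 value, which is measured after randomization.

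The cost is a short edit to the analysis plan and no new data. The model uses one more degree of freedom: with 100 CGM patients, 97 becomes 96, or about 1% of error variance.
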